Russian Federation	037	152	B
Russian Federation	038	300	A
Russian Federation	038	992	B
Russian Federation	038	840	B
Russian Federation	038	230	A
Russian Federation	039	985	B
Russian Federation	039	946	A
Russian Federation	039	769	A
Russian Federation	039	522	B
Russian Federation	040	736	B
Russian Federation	040	808	A
Russian Federation	040	431	B
Russian Federation	040	495	A

Version 1.0 of 12.11.2021

Protocol-Specific Version for Protocol #PHS-
APIS-004-MEX-SOL-TAV. version 1.3 dated
07.06.2021

CONFIDENTIAL

page 17 of 58

Plan for statistical analysis of efficacy and safety parameters

Country	Block number	Randomization code	Therapy
Russian Federation	041	137	B
Russian Federation	041	970	A
Russian Federation	041	905	A
Russian Federation	041	715	B
Russian Federation	042	215	A
Russian Federation	042	508	B
Russian Federation	042	774	A
Russian Federation	042	832	B
Russian Federation	043	713	A
Russian Federation	043	782	B
Russian Federation	043	250	B
Russian Federation	043	432	A
Russian Federation	044	501	B
Russian Federation	044	845	A
Russian Federation	044	960	A
Russian Federation	044	667	B
Russian Federation	045	570	B
Russian Federation	045	903	A
Russian Federation	045	257	B
Russian Federation	045	943	A
Russian Federation	046	413	B
Russian Federation	046	857	A
Russian Federation	046	218	A
Russian Federation	046	825	B
Russian Federation	047	500	A
Russian Federation	047	650	B
Russian Federation	047	875	A
Russian Federation	047	849	B
Russian Federation	048	227	B
Russian Federation	048	976	A
Russian Federation	048	220	A
Russian Federation	048	165	B
Russian Federation	049	696	B
Russian Federation	049	379	A
Russian Federation	049	403	A

Version 1.0 of 12.11.2021

Protocol-Specific Version for Protocol #PHS-
APIS-004-MEX-SOL-TAV. version 1.3 dated
07.06.2021

CONFIDENTIAL

page 18 of 58

Plan for statistical analysis of efficacy and safety parameters

Country	Block number	Randomization code	Therapy
Russian Federation	049	147	B
Russian Federation	050	582	B
Russian Federation	050	157	A
Russian Federation	050	539	B
Russian Federation	050	642	A
Russian Federation	051	831	B
Russian Federation	051	884	A
Russian Federation	051	504	B
Russian Federation	051	727	A
Russian Federation	052	270	A
Russian Federation	052	210	B
Russian Federation	052	895	A
Russian Federation	052	120	B
Russian Federation	053	102	A
Russian Federation	053	380	B
Russian Federation	053	239	A
Russian Federation	053	466	B
Russian Federation	054	624	A
Russian Federation	054	229	B
Russian Federation	054	996	A
Russian Federation	054	768	B
Russian Federation	055	815	A
Russian Federation	055	640	B
Russian Federation	055	339	B
Russian Federation	055	562	A
Russian Federation	056	887	B
Russian Federation	056	338	A
Russian Federation	056	378	B
Russian Federation	056	942	A
Russian Federation	057	867	B
Russian Federation	057	837	A
Russian Federation	057	918	A
Russian Federation	057	264	B
Russian Federation	058	232	B
Russian Federation	058	945	A

Version 1.0 of 12.11.2021

Protocol-Specific Version for Protocol #PHS-
APIS-004-MEX-SOL-TAV. version 1.3 dated
07.06.2021

CONFIDENTIAL

page 19 of 58

Plan for statistical analysis of efficacy and safety parameters

Country	Block number	Randomization code	Therapy
Russian Federation	058	363	B
Russian Federation	058	627	A
Russian Federation	059	981	A
Russian Federation	059	353	B
Russian Federation	059	209	B
Russian Federation	059	112	A
Russian Federation	060	765	B
Russian Federation	060	256	A
Russian Federation	060	904	B
Russian Federation	060	163	A
Russian Federation	061	162	A
Russian Federation	061	779	B
Russian Federation	061	776	A
Russian Federation	061	939	B
Russian Federation	062	991	B
Russian Federation	062	263	A
Russian Federation	062	520	A
Russian Federation	062	325	B
Russian Federation	063	899	A
Russian Federation	063	590	B
Russian Federation	063	533	B
Russian Federation	063	327	A
Russian Federation	064	222	A
Russian Federation	064	592	B
Russian Federation	064	871	B
Russian Federation	064	168	A
Russian Federation	065	979	B
Russian Federation	065	659	A
Russian Federation	065	474	A
Russian Federation	065	299	B
Russian Federation	066	308	A
Russian Federation	066	587	B
Russian Federation	066	318	B
Russian Federation	066	407	A
Russian Federation	067	494	B

Version 1.0 of 12.11.2021

Protocol-Specific Version for Protocol #PHS-
APIS-004-MEX-SOL-TAV. version 1.3 dated
07.06.2021

CONFIDENTIAL

page 20 of 58

Plan for statistical analysis of efficacy and safety parameters

Country	Block number	Randomization code	Therapy
Russian Federation	067	527	A
Russian Federation	067	645	B
Russian Federation	067	212	A
Russian Federation	068	878	B
Russian Federation	068	658	A
Russian Federation	068	702	B
Russian Federation	068	812	A
Russian Federation	069	345	B
Russian Federation	069	361	A
Russian Federation	069	775	B
Russian Federation	069	201	A
Russian Federation	070	657	A
Russian Federation	070	397	B
Russian Federation	070	543	A
Russian Federation	070	401	B
Russian Federation	071	730	B
Russian Federation	071	343	A
Russian Federation	071	559	A
Russian Federation	071	980	B
Russian Federation	072	646	A
Russian Federation	072	418	B
Russian Federation	072	851	B
Russian Federation	072	261	A
Russian Federation	073	585	B
Russian Federation	073	506	A
Russian Federation	073	490	A
Russian Federation	073	692	B
Russian Federation	074	799	B
Russian Federation	074	489	A
Russian Federation	074	178	B
Russian Federation	074	243	A
Russian Federation	075	967	B
Russian Federation	075	673	A
Russian Federation	075	862	B
Russian Federation	075	346	A

Version 1.0 of 12.11.2021

Protocol-Specific Version for Protocol #PHS-
APIS-004-MEX-SOL-TAV. version 1.3 dated
07.06.2021

CONFIDENTIAL

page 21 of 58

Plan for statistical analysis of efficacy and safety parameters

Country	Block number	Randomization code	Therapy
Russian Federation	076	630	B
Russian Federation	076	644	A
Russian Federation	076	436	A
Russian Federation	076	792	B
Russian Federation	077	963	B
Russian Federation	077	240	A
Russian Federation	077	689	A
Russian Federation	077	150	B
Russian Federation	078	265	B
Russian Federation	078	433	A
Russian Federation	078	451	B
Russian Federation	078	534	A
Russian Federation	079	948	B
Russian Federation	079	940	A
Russian Federation	079	564	B
Russian Federation	079	858	A
Russian Federation	080	183	A
Russian Federation	080	479	B
Russian Federation	080	485	B
Russian Federation	080	748	A
Russian Federation	081	384	A
Russian Federation	081	586	B
Russian Federation	081	575	A
Russian Federation	081	368	B
Russian Federation	082	593	B
Russian Federation	082	883	A
Russian Federation	082	916	A
Russian Federation	082	224	B
Russian Federation	083	944	B
Russian Federation	083	990	A
Russian Federation	083	625	A
Russian Federation	083	952	B
Russian Federation	084	499	A
Russian Federation	084	108	B
Russian Federation	084	698	B

Version 1.0 of 12.11.2021

Protocol-Specific Version for Protocol #PHS-APIS-004-MEX-SOL-TAV. version 1.3 dated 07.06.2021

CONFIDENTIAL

page 22 of 58

Plan for statistical analysis of efficacy and safety parameters

Country	Block number	Randomization code	Therapy
Russian Federation	084	607	A
Russian Federation	085	675	A
Russian Federation	085	733	B
Russian Federation	085	669	A
Russian Federation	085	783	B
Russian Federation	086	679	A
Russian Federation	086	472	B
Russian Federation	086	115	A
Russian Federation	086	597	B
Russian Federation	087	289	B
Russian Federation	087	726	A
Russian Federation	087	594	A
Russian Federation	087	313	B
Russian Federation	088	563	A
Russian Federation	088	268	B
Russian Federation	088	710	B
Russian Federation	088	124	A
Russian Federation	089	158	B
Russian Federation	089	376	A
Russian Federation	089	387	B
Russian Federation	089	388	A
Russian Federation	090	856	A
Russian Federation	090	237	B
Russian Federation	090	879	A
Russian Federation	090	236	B
Russian Federation	091	182	A
Russian Federation	091	629	B
Russian Federation	091	889	B
Russian Federation	091	558	A
Russian Federation	092	719	A
Russian Federation	092	553	B
Russian Federation	092	245	B
Russian Federation	092	292	A
Russian Federation	093	414	B
Russian Federation	093	618	A

Version 1.0 of 12.11.2021

Protocol-Specific Version for Protocol #PHS-
APIS-004-MEX-SOL-TAV. version 1.3 dated
07.06.2021

CONFIDENTIAL

page 23 of 58

Plan for statistical analysis of efficacy and safety parameters

Country	Block number	Randomization code	Therapy
Russian Federation	093	516	A
Russian Federation	093	781	B
Russian Federation	094	544	B
Russian Federation	094	880	A
Russian Federation	094	763	B
Russian Federation	094	475	A
Russian Federation	095	331	B
Russian Federation	095	614	A
Russian Federation	095	722	A
Russian Federation	095	478	B
Russian Federation	096	739	B
Russian Federation	096	833	A
Russian Federation	096	755	A
Russian Federation	096	271	B
Russian Federation	097	389	A
Russian Federation	097	668	B
Russian Federation	097	525	A
Russian Federation	097	752	B
Russian Federation	098	842	A
Russian Federation	098	284	B
Russian Federation	098	660	B
Russian Federation	098	826	A
Russian Federation	099	352	A
Russian Federation	099	794	B
Russian Federation	099	143	B
Russian Federation	099	532	A
Russian Federation	100	246	B
Russian Federation	100	135	A
Russian Federation	100	589	B
Russian Federation	100	443	A
Russian Federation	101	211	A
Russian Federation	101	322	B
Russian Federation	101	834	B
Russian Federation	101	446	A
Russian Federation	102	805	A

Version 1.0 of 12.11.2021

Protocol-Specific Version for Protocol #PHS-
APIS-004-MEX-SOL-TAV. version 1.3 dated
07.06.2021

CONFIDENTIAL

page 24 of 58

Plan for statistical analysis of efficacy and safety parameters

Country	Block number	Randomization code	Therapy
Russian Federation	102	312	B
Russian Federation	102	966	A
Russian Federation	102	604	B
Russian Federation	103	277	A
Russian Federation	103	511	B
Russian Federation	103	176	A
Russian Federation	103	114	B
Russian Federation	104	915	B
Russian Federation	104	423	A
Russian Federation	104	647	A
Russian Federation	104	550	B
Russian Federation	105	753	B
Russian Federation	105	571	A
Russian Federation	105	634	A
Russian Federation	105	914	B
Russian Federation	106	686	A
Russian Federation	106	113	B
Russian Federation	106	369	A
Russian Federation	106	159	B
Russian Federation	107	852	B
Russian Federation	107	684	A
Russian Federation	107	390	A
Russian Federation	107	622	B
Russian Federation	108	674	B
Russian Federation	108	778	A
Russian Federation	108	947	A
Russian Federation	108	969	B
Russian Federation	109	596	B
Russian Federation	109	751	A
Russian Federation	109	438	A
Russian Federation	109	591	B
Russian Federation	110	666	B
Russian Federation	110	541	A
Russian Federation	110	295	A
Russian Federation	110	106	B

Version 1.0 of 12.11.2021

Protocol-Specific Version for Protocol #PHS-
APIS-004-MEX-SOL-TAV. version 1.3 dated
07.06.2021

CONFIDENTIAL

page 25 of 58

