4.3.2. Randomization

After the patient (his/her legal representative) signs the Informed Consent Form at the screening stage, he/she is assigned a screening number of the form XXXYYYY, where XX is the number of the investigational site (e.g. 01, 02, 03), YYY is the patient's serial number (starting from 001), according to the order of inclusion (3 digits). If, after all the procedures planned as part of the screening, the investigator decides that the patient can take part in the trial, the patient is randomized.

randomization (an allocation method according to probability theory) is necessary to minimise subjectivity in assigning patients to therapy groups.

The randomization code will be presented in a three-digit format of the form RRR and will be assigned to each screened patient who meets the inclusion/non-inclusion criteria.

Allocation of patients to therapy groups will be done in a 1:1 ratio.

The randomization procedure, assigning a randomization number to the patient will be done after all screening procedures have been carried out before prescribing the IP.

The randomization code of each patient must be compulsorily recorded in the patient's source documentation and CRF.

If a patient early terminates the trial (is excluded from the trial for any reason), his/her randomization code will not be reused.

Randomization will be carried out centrally. For the implementation of centralized randomization (electronic randomization system) it is planned to use an automated communication system over the Internet - Interactive Web Response System (IWRS). Once the Investigator enters the patient data, the number will be generated automatically by the system.

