4.7. Storage and disclosure of randomization /screening numbers

The double-blinding condition is observed throughout the trial. The randomization code for a particular patient should be prematurely disclosed in the following cases:

- occurrence of an insured event, if the qualification of the event requires information about the type of prescribed therapy;
- sponsor's decision;
- written request from the local ethics committee supervising the trial;
- decision of regulatory authorities (Ministry of Health, Ethics Council under the Ministry of Health of the Russian Federation, Federal Service for Surveillance in Healthcare, other regulatory body authorized in accordance with the established procedure to control the conduct of clinical studies).

If it is necessary to disclose the code, the investigator performs the unblinding procedure according to the instructions received prior to the trial.

A complete list of all screening/randomization numbers used in the trial and their corresponding therapy is a confidential document, kept by the authorized representative and used to monitor the conduct of the trial.

The Investigator should ensure that the anonymity of the patients is respected. In the CRF, patients are identified only by assigned numbers.

The Investigator must maintain documentation containing patient number information, stored in accordance with the rules applicable to confidential documents.

The Investigator must also maintain in strict confidence documents not intended to be handed over to the Sponsor, particularly signed Patient Information Sheets with the Informed Consent Forms.

4.8. A list of all data recorded directly in the CRF and considered as source data

This trial does not contain data to be entered directly into the CRF without initially recording such information in source documentation.

All information that is recorded in the CRF is previously entered into the patient's source medical documentation - the patient's medical record, blood and urine laboratory test forms, ECG forms, etc. An electronic data collection system can also be used to collect source data (e.g. results of specialized scales).

5. Selection and exclusion of trial participants

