Statistical evaluation of efficacy and safety parameters will be performed in accordance with the Drug Evaluation Guidelines (Volume I. - FGBU NCESMP, Moscow, 2014), Guidelines on the principles of application of biostatistics in clinical trials of medicinal products (Annex to the recommendation of the EEC Collegium from 03.11.2020 No. 2014) and general recommendations on biomedical statistics (ICH Topic E9 Statistical Principles for Clinical Trials, CPMP/ICH/363/96, 1998; Sergienko V.I., Bondareva I.B. Mathematical Statistics in Clinical Trials, Moscow: GEOSTAR-Media, 2006).

3. Deviations from protocol

A statistical plan has been prepared and will be agreed prior to the statistical analysis. Statistical analyses were planned according to the Clinical Trial Protocol. Deviations from the protocol in statistical analyses are not planned. Any deviation from the protocol is permitted only in an emergency or after written authorization from the Sponsor. If there is a deviation from the planned statistical analysis, all changes will be identified compared to the methods described in the statistical analysis plan. Similarly, if any additional changes are required after the analysis has been performed, this will be reflected in the Clinical Trial Report. All deviations of the present from the statistical analysis plan with their justification will be reported in the Clinical Trial Report. No changes will be made to the list of parameters to be evaluated. Statistical analysis methods may be changed if this would facilitate a more correct and informative analysis, any changes will be described and justified in the final Clinical Trial Report.

Version 1.0 of 12.11.2021

[figure not shown]
Protocol-Specific Version for Protocol #PHS-APIS-004-MEX-SOL-TAV. version 1.3 dated 07.06.2021

CONFIDENTIAL

page 12 of 58

Plan for statistical analysis of efficacy and safety parameters

4. Trial procedures

5. Randomization

Table 1. Randomization scheme developed by Smooth Drug Development

Country	Block number	Randomization code	Therapy
Republic of Kazakhstan	001	616	B
Republic of Kazakhstan	001	174	A
Republic of Kazakhstan	001	637	B
Republic of Kazakhstan	001	869	A
Republic of Kazakhstan	2	455	A
Republic of Kazakhstan	2	548	B
Republic of Kazakhstan	2	687	A
Republic of Kazakhstan	2	809	B
Republic of Kazakhstan	3	810	B
Republic of Kazakhstan	3	680	A
Republic of Kazakhstan	3	294	A
Republic of Kazakhstan	3	513	B
Republic of Kazakhstan	4	180	A
Republic of Kazakhstan	4	467	B

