**Plan for statistical analysis of efficacy and safety parameters**

Country	Block number	Randomization code	Therapy
Russian Federation	111	123	B
Russian Federation	111	100	A
Russian Federation	111	139	A
Russian Federation	111	631	B
Russian Federation	112	302	A
Russian Federation	112	206	B
Russian Federation	112	349	A
Russian Federation	112	420	B
Russian Federation	113	359	B
Russian Federation	113	430	A
Russian Federation	113	797	B
Russian Federation	113	780	A
Russian Federation	114	740	A
Russian Federation	114	457	B
Russian Federation	114	860	A
Russian Federation	114	577	B
Russian Federation	115	606	B
Russian Federation	115	122	A
Russian Federation	115	549	A
Russian Federation	115	288	B

Therapy A - Investigational product solution for intravenous and intravenous administration and investigational product film-coated tablets;

Therapy B - Placebo 1 solution for intravenous and intravenous administration and Placebo 2 film-coated tablets.

6. Main and additional trial parameters to be assessed in the course of the trial

The ITT, mITT and PP populations will be used for efficacy analyses, with the PP population planned to be used as the main population.

The following indicator has been chosen as the **primary efficacy criterion**:

The magnitude of change in the patient's mRS (Modified Rankin Scale) score at the end of therapy vs. baseline (in scores).

The following indicators were selected as **secondary** endpoints:

- The magnitude of change in the patient's mRS (Modified Rankin Scale) score at the end of parenteral therapy vs. baseline (in scores).
- Proportion of disabled patients (mRS score 3 or more) at the end of therapy vs. baseline;
- Proportion of disabled patients (mRS score 3 or more) at the end of parenteral therapy vs. baseline;

Version 1.0 of 12.11.2021

Protocol-Specific Version for Protocol #PHS-APIS-004-MEX-SOL-TAV. version 1.3 dated 07.06.2021

CONFIDENTIAL

page 26 of 58

Plan for statistical analysis of efficacy and safety parameters

- The magnitude of change in the patient's NIHSS (National Institutes of Health Stroke Scale) score at the end of therapy vs. baseline (in scores).
- The magnitude of change in the patient's NIHSS (National Institutes of Health Stroke Scale) score at the end of parenteral therapy vs. baseline (in scores).
- The magnitude of change in the patient's MoCA cognitive status score at the end of therapy vs. baseline (in scores).

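### SAP Table 1 prints the whole randomisation list with its A/B key, against the custody rule in Protocol 4.7, and every block in it is two consecutive A/B pairs

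*SAP*

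**What the plan says.** SAP section 5 contains Table 1, "Randomization scheme developed by Smooth Drug Development". Each row gives country, block number, a three-digit code and a therapy letter. It runs from "Republic of Kazakhstan 001 616 B" to the block that opens with "Russian Federation 115 606 B". The key follows directly: "Therapy A - Investigational product solution for intravenous and intravenous administration and investigational product film-coated tablets" and "Therapy B - Placebo 1 solution for intravenous and intravenous administration and Placebo 2 film-coated tablets".

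Protocol 4.7 says the double blind is kept for the whole trial, restricts code breaks to listed cases, and states: "A complete list of all screening/randomization numbers used in the trial and their corresponding therapy is a confidential document". An authorised representative keeps that list.

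Protocol 4.3.2 describes randomisation as central, through an IWRS that issues the number automatically. On balance it says only: "Allocation of patients to therapy groups will be done in a 1:1 ratio". It also requires each patient's randomisation code to be entered in the source documents and the CRF. Neither document states in words a block size, a within-block restriction or stratification by country; these can only be read from Table 1.

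**The concern.** There are two separate weaknesses.

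**The printed key.** The code is in the CRF and the SAP turns that code into a treatment, so a person with both is unblinded without any inference. This matters because several steps that shape the primary result leave room for judgement:

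- The primary analysis is in the PP population (Protocol 9.7.2).
- A patient can be withdrawn on the investigator's or sponsor's decision about a deviation, or on the investigator's judgement (Protocol 5.3, items 4 and 5).
- Deviations thought able to affect the efficacy assessment remove a patient from PP (Protocol 9.3).
- The sponsor decides case by case on visits outside their time limits (Protocol 11.8).
- The statistician and Principal Investigator screen the database for questionable data (Protocol 9.10).

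SAP section 9 wants processing by staff outside patient management so that evaluation is independent. A decoded list inside the SAP works against that aim.

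**The pair pattern.** The block numbering suggests permuted blocks of four. If the second and fourth code of each block are always the opposite of the code before, the list protects less than it appears to.

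**Working it through.** **Inputs.** All rows of SAP Table 1, read in list order; the 1:1 ratio from Protocol 4.3.2; 304 planned randomisations from Protocol 9.1 and SAP section 8.

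**1. Reproduce the list's stated properties.** There are 115 blocks of four codes, so 115 × 4 = 460 codes, with no code repeated. Kazakhstan has blocks 1–5 (20 codes), Uzbekistan blocks 6–10 (20) and the Russian Federation blocks 11–115 (105 × 4 = 420). The letters total 230 A and 230 B, so the 1:1 ratio is met. Labels such as 17 and 017 differ only in formatting.

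**2. Count the order within blocks.**

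| Pattern | Count |
|---|---|
| BAAB | 36 |
| BABA | 29 |
| ABBA | 26 |
| ABAB | 24 |
| AABB | 0 |
| BBAA | 0 |
| Total | 115 |

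All 230 pairs (positions 1–2 and 3–4) hold one A and one B. This is true in each country: 5 of 5, 5 of 5 and 105 of 105 blocks.

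**3. Compare with blocks of four drawn from all six orders.**

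- Expected AABB or BBAA: 115 × 2/6 = 38.3. Observed: 0.
- Chance of none: (4/6)^115 = 5.6 × 10⁻²¹.
- Equal frequency of the four orders seen: 115/4 = 28.75 expected in each; chi-square = (7.25² + 0.25² + 2.75² + 4.75²)/28.75 = 2.88 on 3 df, p = 0.41. This is what independent blocks of two would give.

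**4. What the pattern changes.**

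| Quantity | True blocks of 4 | Table 1 |
|---|---|---|
| Share of allocations fixed by earlier ones in the block | (1 + 1/3)/4 = 33% | 2/4 = 50% |
| Best-guess hit rate if all earlier allocations are known | (1/2 + 2/3 + 2/3 + 1)/4 = 71% | (1/2 + 1)/2 = 75% |
| Probability that the pair-mate is the opposite arm, given one allocation and its position | 2/3 | 1 |

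**5. The printed key.** No arithmetic is needed. Protocol 4.3.2 puts the code in the CRF, SAP Table 1 maps code to letter, and the key maps letter to product. Chained together, they decode every patient, whatever the block size.

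**6. Room to act.** 460 − 304 = 156 codes would remain after full first-stage enrolment. Protocol 9.1 and 9.9 foresee a second stage if calculated power is below 80%.

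**The case against.** The strongest reply is that the pattern could hardly be used at a site. The IWRS issues codes centrally. Codes are scrambled three-digit numbers that reveal neither order nor pairing. The sequence runs by country, so the pair-mate may be at another site. Packaging is blinded (Protocol 4.3.1), code breaks are limited to listed cases and concern a particular patient, and the listed side effects of both products are all very rare. The 50% and 75% figures hold only for someone who knows the earlier allocations and their order; without that, guessing is 50% under either scheme, and even with it the gain is 4 percentage points. All of this stands. No stated rule is broken either, because neither document promises unrestricted blocks of four.

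A reader might infer that allocation was predictable in practice, or that the primary result is biased. The documents do not support either inference. They show a weakness in concealment and no instance of its use. They also do not name who rates the mRS, so an argument through rater bias would rest on an assumption.

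On the key, one can answer that the SAP is marked confidential on its pages and that Protocol 4.3.1 lists only the patient, the investigator and laboratory staff as blinded. This narrows the conflict but does not remove it. Protocol 4.7 sets custody as well as confidentiality, and an analysis plan is a working document for people other than the list's custodian.

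Finally, issuing new code numbers could clash with supplies already labelled, since Protocol 11.8 counts a mismatch between code and pack label among its examples of significant deviations. That objection is right, and the fix below avoids it.

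**Conclusion.** The point holds as a concealment weakness with two parts. The printed list and key are the more material part: all 460 codes can be decoded from the SAP, contrary to the custody rule in Protocol 4.7, in a trial whose primary analysis set depends partly on discretionary exclusions. The pair pattern is exact (115 of 115 blocks) and undisclosed, but its effect is conditional. It raises certainty about a pair-mate from 2/3 to 1 only if one allocation and its list position become known.

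Assumptions: Table 1 is the list loaded in the IWRS, some codes are still unallocated, and the SAP is read by people other than the list's custodian. The documents state none of these. The SAP is version 1.0, written for protocol version 1.3; the comparison here is with Protocol 4.7 as it stands in version 1.5.

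**What to change.** 1. Remove Table 1 and the A/B key from the SAP. Hold them as a restricted file outside the analysis and site teams until database lock, and record who has already had access. In their place, describe the block scheme and country stratification in general terms. Cost: one SAP edit.
2. For codes not yet allocated, including any second-stage patients, re-sequence the existing code–therapy pairs within country into mixed blocks of 4 and 6 drawn from all permutations, and load the new order in the IWRS. Codes keep their therapy, so pack labels stay valid. Cost: one list upload, and an imbalance of up to 3 patients per country at any time (at most 1 now). This cures the pair pattern only. Anyone who already holds Table 1 can still decode a code, which is why the access record in step 1 is needed.
3. State in the clinical trial report that the codes already used were pair-balanced within country. Cost: one sentence.

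If no unused codes remain, or Table 1 is not the live list, step 2 falls away. Step 1 still applies, and step 3 applies if the codes used came from this list.
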